3.7 Study Schema

4. STUDY PROCEDURES

4.1 Duration of Treatment

Treatment will continue from presentation in the ED or PPU to the transfer of care home to the parents/legal guardians.

4.2 Follow up

An investigator will attend telephone follow-up on the first working day after the infant is 15 days post-discharge. The parent/legal guardian will be contacted and asked 7 set survey questions to determine whether an adverse event under therapeutic goods administration requirements, and the treatment has been successful post-discharge (Appendix 2). The investigator will record any identified adverse events relating to the study devices, and the infant will be followed up further if it is clinically indicated.

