Heart rate (beat per min)†	X	X	X	X	X	X	X	X	X	
Respiratory rate (breath per min)†	X	X	X	X	X	X	X	X	X	
Arterial blood pressure (mmHg)†	X	X	X	X	X	X	X	X	X	
Clinical respiratory score†	X	X	X	X	X	X	X	X	X	
PCR	X									
Blood sample*	X									
VBG*	X			X						
Concomitant Medications	X	X	X	X	X	X	X	X	X	
Medical treatment‡	X	X	X	X	X	X	X	X	X	
Adverse event record	X	X	X	X	X	X	X	X	X	

If the patient was not discharged after 96 hours, the procedures mentioned above were continued.

†All parameters were measured during the resting of children.

*Samples were performed at any time if the clinician deemed it necessary.

Protocol No 1
Date: 10/03/2017
Revised 1: 10/03/2020
Revised 2:14/02/2021

**All children included in the study were phoned after 15 days post-discharge.

†The clinician decides to use medical treatments such as beta2 agonist, systemic steroid, and hypertonic saline.

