2.4 Safety Objectives

- ✓ The proportion of the treatment failure at 4 hours and escalation of care
- ✓ The proportion of the admission of ICU for IMV
- ✓ The proportion of adverse events

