3.4 Withdrawal Criteria

Consenting parents/legal guardians will be informed that they have the opportunity of withdrawing their infant/s from the study at any time with no explanation. Data generated by the drawn infant/s will be censored at the time of withdrawal. They will remain part of the study and will be analyzed by intention to treat and per-protocol approach for adherent patients to their protocol. Withdrawn children who require ongoing supplemental oxygen will receive the standard care for bronchiolitis, and no additional data will be collected after withdrawal.

[figure not shown]

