6. SAFETY AND ADVERSE EVENT(S)

During the study, AEs, regardless of relatedness to the study device, will be reported on the AE page of the CRF (Appendices 4). All adverse reactions will be recorded in CRF and registered in the manuscript and clinicaltrial.gov. Open disclosure is paramount to the ongoing efficacy and ethical conduct of the trial, so parents/ legal guardians of participants experiencing AE are to be entirely briefed about the nature and effect of the AE. They are to be informed of likely consequences and alternative facts considered relevant following the standard disclosure duty.

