6.2 Follow-up 15 days safety assessment

On the initial business day after 15 days, post-discharge an investigator will contact the parent/legal guardian to ask about any AE which may have occurred following the infant's return home under any medical administrations' requirements.

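### Section 4.2 ties AE recording at the 15-day call to device-related events, against sections 6 and 6.2; separately, section 3.4 ends all safety data at withdrawal

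*Combined protocol and SAP*

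**What the plan says.** Three places govern AEs at the 15-day call.

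- Section 6, the general rule: "AEs, regardless of relatedness to the study device, will be reported on the AE page of the CRF".
- Section 6.2, the purpose of the call: "to ask about any AE which may have occurred following" the child's return home.
- Section 4.2, what is written down at that call: "The investigator will record any identified adverse events relating to the study devices".

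Section 6 then adds a second rule in a different term: "All adverse reactions will be recorded in CRF and registered in the manuscript and clinicaltrial.gov". Section 6.1 defines an adverse reaction as an event caused by a drug, so this sentence is narrower than the one before it.

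The outcome in section 2.4 is "The proportion of adverse events", with no relatedness limit, time window or per-child definition. Section 7.2 compares it between arms by Fisher's exact test with an odds ratio and 95% CI, as it does ICU admission. Section 3.6 states that clinicians, parents and investigators cannot be blinded.

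On withdrawal, section 3.4 censors the child's data at that time and states that "no additional data will be collected after withdrawal". It also keeps the child in the study for analysis by intention to treat.

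**The concern.** Two investigators could each follow the protocol and record different events from the same call. A readmission on day 10 after discharge that is judged unrelated to the oxygen device is reportable under section 6, but falls outside the recording instruction in 4.2. The person making that judgement knows the arm, and may judge differently for high flow than for a simple mask. The blinded biostatistician cannot recover an event that was never recorded.

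The withdrawal rule is a different problem with a similar result. It is a gap in follow-up, not a relatedness filter. In an open trial, a parent may withdraw a child because the child is worse or does not tolerate the device. If that child is later admitted to ICU, a tested safety outcome has no way to include it. The harm-based stopping provision in the Statistical Analysis Plan paragraph also depends on what is recorded.

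**Working it through.** **Text check.** The plan states no AE rate, so there is no figure to reproduce.

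| Place | Which AEs | Period |
|---|---|---|
| Section 6 | All, related or not | During the study |
| Section 6.2 | Any | After discharge, asked at the call |
| Section 4.2 | Those relating to the study devices | Recorded at the same call |
| Section 3.4 | None | After withdrawal |
| Section 7.2 | Not defined | Not defined |

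Sections 4.2 and 6.2 describe one call with two scopes. Before discharge only section 6 applies, so a relatedness filter can act only on post-discharge events. It reaches the tested proportion only if those events count in it, which 7.2 does not say. Appendix 4, as shown, does not settle the matter: where section 6 points to an AE page, it has a yes/no complications item with free text, and no visible relatedness or post-discharge field.

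**Illustration of size.** From the plan: 55 children per arm, Fisher's exact test, two-sided 0.05. Assumed, because the documents give no values: in-hospital AE risk p of 5% or 10%; post-discharge AE risk q of 5%, 10% or 20%; both equal in the two arms and independent within a child; and a share r of post-discharge AEs that is recorded.

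Recorded proportion = 1 − (1 − p)(1 − q·r). The odds ratio is the ratio of the two arms' odds of a recorded AE. Rejection probabilities come from full enumeration of the two binomials.

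Example with p = 5%, q = 20%, r = 75% in one arm and 25% in the other:
- 1 − 0.95 × (1 − 0.15) = 0.1925
- 1 − 0.95 × (1 − 0.05) = 0.0975
- OR = (0.1925/0.8075) / (0.0975/0.9025) = 2.21

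| p | q | True, each arm | Recorded, r = 75% | Recorded, r = 25% | Spurious OR | Fisher rejection |
|---|---|---|---|---|---|---|
| 5% | 5% | 9.8% | 8.6% | 6.2% | 1.42 | 2.69% |
| 5% | 10% | 14.5% | 12.1% | 7.4% | 1.73 | 6.64% |
| 5% | 20% | 24.0% | 19.3% | 9.8% | 2.21 | 20.19% |
| 10% | 5% | 14.5% | 13.4% | 11.1% | 1.23 | 3.15% |
| 10% | 10% | 19.0% | 16.7% | 12.3% | 1.44 | 5.83% |
| 10% | 20% | 28.0% | 23.5% | 14.5% | 1.81 | 15.47% |

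With full recording in both arms, rejection is 1.94% to 3.05%. With r = 25% in both arms the odds ratio stays at 1, but the recorded proportion falls to between 6.2% and 14.5%.

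Equal under-recording can also hide real harm. With p = 5% in both arms and an assumed true q of 30% versus 5%, power is 82% at full recording, 34% at r = 50% and 10% at r = 25%.

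**Withdrawal.** A Fisher test needs a yes or no for each child. Section 3.4 supplies a record that stops at withdrawal, and 7.2 does not say whether such a child counts as event-free or is left out. Either way, a later event is absent. No size is computed: the 10% attrition in 7.1 is attached to the longitudinal aspect of the study and is not stated to be withdrawal.

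**The case against.** The strongest reply is that section 6 is the governing rule and already covers every AE. Section 4.2 does not say that unrelated events are to be ignored, and the sentence before the quoted one has the survey establish whether an adverse event occurred. This limits the point but does not remove it: a recording instruction qualified by relatedness still differs from one that sets relatedness aside, and nothing says which prevails.

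Some stronger readings are tempting and are not supported.

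- A reader might infer that the whole compared AE proportion is filtered by relatedness. In-hospital events fall under section 6, so this does not follow.
- A reader might infer a bias against one arm. The CRF lists both St-FMOT and HFNCOT as the study device, so the wording of 4.2 covers both arms. Nothing shows differential judgement or its direction.
- A reader might take the schedule as omitting AE recording at the call. In the table as read, the only mark in the phone column sits in the inclusion/exclusion row, so that column is not reliable evidence. The table's footnote and sections 4.2 and 6.2 establish that the call takes place.
- A reader might treat worsening as loss to follow-up. Section 5.3 keeps deteriorating children in the trial through rescue and ICU pathways; the gap arises only when a parent withdraws the child.

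It is also fair to say that the AE proportion is not a primary outcome, and that the sample size and primary comparisons are untouched.

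**Conclusion.** The conflict between 4.2 and sections 6 and 6.2 stands. Following 4.2 may drop unrelated-judged AEs after discharge, through an unblinded judgement. The gap after withdrawal in 3.4 also stands, whichever way 4.2 is read.

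The size is unknown. Under the assumed risks and a 75% versus 25% difference in recording, the spurious odds ratio is about 1.2 to 2.2 and Fisher rejection with no true difference is 2.7% to 20.2%. If recording is equally incomplete in both arms, the result is an under-count and lost power, not a spurious difference. All of this requires that post-discharge AEs count in the tested proportion. The point should be corrected because it concerns tested safety outcomes in an open-label trial and the remedy is cheap.

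**What to change.** 1. In 4.2, replace the recording rule so that every AE, readmission and death is recorded, related or not, in both arms, in line with 6 and 6.2. Hold relatedness in a separate field worded for a device.
2. Add an AE entry for the 15-day call to the CRF in Appendix 4, and confirm that the AE row of the schedule covers the call.
3. In 7.2, define the compared outcome as children with at least one AE from randomisation to the 15-day call.
4. In 3.4, separate stopping study treatment from refusing further data. Keep ICU admission, IMV, AEs and the 15-day call for withdrawn children unless the parent also refuses this, and report refusals by arm.

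The cost is protocol and consent wording plus a form field, around a call already planned. More unrelated minor events will be listed, and some parents will refuse the safety contact. The sample size does not change.

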5. STUDY TREATMENT PLAN

Study procedures will be individually documented in the case report form, available in ED and PPU. This trial will not introduce any invasive procedure or investigation not usually attended as standard care.

5.1 Investigational Treatments

Children will receive maximum therapy for 4 hours, which means that children receive at a flow rate of 2 L*kg/min, but we will let the FiO₂ reduce if children give an excellent response to the treatment. For children on St-FMOT, the FiO₂ will be reduced at any time if children provide a suitable response to the treatment, and the oxygen requirement will be controlled by turning off the flow every hour. Reducing the flow rate should be considered after 4 hours if the children's observations for HR, RR, retraction, SpO₂, feeding ability and tolerability, CRS, and PEWS stabilize or decrease.

➤ **Control Arm:** Children in the standard-therapy group received supplemental oxygen via a simple face mask, a range of 6-10 L/min, to maintain a SpO₂ level between 92-98%. Those who sustained the SpO₂ >92% in the ambient oxygen concentration were weaned off St-FMOT.

5.2 Experimental Arm: Children in the high-flow group received heated and humidified high-flow oxygen at a rate of 2 L*kg/min (maximum 25 L/min), using an age-appropriate Optiflow Junior cannula and Airvo 2 high-flow system (Fisher and Paykel Healthcare). The initial FiO₂ was set at

40%. The starting flow rate continued for a minimum of 4 hours. According to the patients' clinical response, the flow rate was decreased by 0.5 L*kg/min per hour. The FiO₂ was adjusted to obtain the SpO₂ levels between 92-98%. When the flow rate was at 0.5 L*kg/min, and the FiO₂ was equal to the ambient oxygen concentration, HFNCOT was stopped.

5.3 Treatment Failure and Escalation of Care

- ✓ The clinician will decide on the escalation of care at any time if the Pediatric Early Warning Score (PEWS) is ≥ 7 points (Appendices 3).
- ✓ Treatment failure at 4 hours is considered when at least three of the following five criteria are present for both groups.
 1. No change or an increase in HR relative to baseline
 2. No change or an increase in RR relative to baseline
 3. Persistence of low SpO₂ ($<92\%$) in the three near independent measurements despite receiving FiO₂ $>40\%$ for HFNCOT and at a maximum 10 L/min for St-FMOT
 4. No change or an increase in CRS relative to baseline
 5. Blood pressure of carbon dioxide >60 mm/Hg
- ✓ Children with treatment failure at 4 hours or who need escalation of care will be treated as follows:
 - **Control Arm:** Children who deteriorate on the St-FMOT will receive HFNCOT (at 2 L*kg/min) as a rescue treatment in the ward or be transferred to the ICU for IMV.
 - **Experimental Arm:** Children who deteriorate on HFNCOT are admitted to the ICU for IMV as a rescue treatment.

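### A child unchanged in HR, RR and CRS at 4 hours is a treatment failure under 5.3, but 5.1 and the rescue lines of 5.3 do not agree on what is then done

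*Combined protocol and SAP*

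**What the plan says.** Section 5.3 sets the definition: "Treatment failure at 4 hours is considered when at least three of the following five criteria are present for both groups". Criteria 1, 2 and 4 are "No change or an increase in HR relative to baseline", "No change or an increase in RR relative to baseline" and "No change or an increase in CRS relative to baseline". Criterion 3 is persistently low SpO2 despite a stated level of oxygen support, and criterion 5 is carbon dioxide above 60.

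The consequence is introduced by "Children with treatment failure at 4 hours or who need escalation of care will be treated as follows". The lines beneath it are narrower. For high flow the text is "Children who deteriorate on HFNCOT are admitted to the ICU for IMV as a rescue treatment". The mask line is also written for children who deteriorate and gives high flow on the ward or transfer to ICU.

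Section 5.1 opens its weaning instruction with "Reducing the flow rate should be considered after 4 hours if the children's observations for HR, RR, retraction" and makes the step depend on seven observations in all, SpO2 among them. The condition on that list closes with the words "feeding ability and tolerability, CRS, and PEWS stabilize or decrease". Section 5.2 ties stepwise flow reduction in the high-flow arm to clinical response after a minimum of 4 hours.

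Four-hour failure is a safety objective (2.4). Section 7.2 compares failure, rescue and ICU admission between arms with Fisher's exact test and odds ratios. The CRF (Appendix 4) records failure as a yes/no box.

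**The concern.** An unchanged child meets a definition that leads to rescue. On the natural reading of a condition that offers stabilizing as the alternative to decreasing, the same HR, RR and CRS also support considering less flow. No section defines stabilizing, gives a tolerance for no change, or says which rule comes first. Section 5.3 is also inconsistent within itself: its lead-in covers every failure, while its two action lines cover only those who get worse.

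At stake are the rescue and ICU counts. An unchanged child may be rescued because the lead-in says so, left alone because he or she has not deteriorated, or considered for weaning under 5.1. Clinicians know the arm, and the prescribed consequence differs by arm: ward high flow or ICU on mask, ICU for IMV on high flow. If the choice among these readings varies by arm, the between-arm comparison of rescue and ICU admission reflects it.

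**Working it through.** The plan gives no figure to reproduce here, so the check is mainly logical.

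**1. The unchanged child under each rule.** Take HR, RR and CRS equal to baseline, adequate SpO2, and carbon dioxide not above 60.
- Failure score (5.3): 1 + 1 + 0 + 1 + 0 = 3 of 5, which is a failure.
- Lead-in to the actions (5.3): applies, because the child is a failure.
- Arm-specific lines (5.3): do not apply as worded, because nothing has deteriorated.
- Flow-reduction condition (5.1): met on HR, RR and CRS if stabilized means unchanged.

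**2. All combinations.** Let HR, RR and CRS each be down, same or up, and let low SpO2 and high carbon dioxide each be absent or present: 3 × 3 × 3 × 2 × 2 = 108 patterns.
- 74 score at least 3 and are failures.
- 16 of those have no rise in HR, RR or CRS, so they also meet 5.1 on these three signs.
- 4 of the 16 are unchanged on all three. The other 12 have at least one sign improved and reach three criteria only with low SpO2 or high carbon dioxide.
- 1 of the 16 has neither low SpO2 nor high carbon dioxide: the child in step 1.

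These are patterns, not frequencies. Section 5.1 also lists retraction, SpO2, feeding and PEWS, which the enumeration does not apply, so 16 is an upper count of the overlap.

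**3. How often this could occur.** The documents give no variability for 4-hour changes. As an illustration, assume a child with no true change, integer-rounded normal changes with mean zero, independence, and a probability p that CRS is not lower. Then P(change = 0) = 2Φ(0.5/SD) − 1, and P(change ≥ 0) = 0.5 + P(change = 0)/2.

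| Assumed SD of HR, SD of RR, p | HR and RR exactly unchanged, CRS not lower | HR, RR and CRS all not lower |
|---|---|---|
| 6, 3, 0.6 | 0.066 × 0.132 × 0.6 = 0.5% | 0.533 × 0.566 × 0.6 = 18% |
| 8, 5, 0.7 | 0.050 × 0.080 × 0.7 = 0.3% | 0.525 × 0.540 × 0.7 = 20% |
| 12, 6, 0.8 | 0.033 × 0.066 × 0.8 = 0.2% | 0.517 × 0.533 × 0.8 = 22% |

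RR is itself a CRS item (Appendix 1), so independence understates the last column. If CRS were never lower when RR is not lower, p drops out and the column becomes 28–30% (for example 0.533 × 0.566 = 30%). A second set of assumptions (symmetric HR and RR changes, probability of an unchanged CRS 0.3–0.8, common correlation 0–0.6) gives 16–35%.

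The two columns answer different questions. The middle one is close to the literal conflict. The last is the chance that a child with no true change meets criteria 1, 2 and 4, and it arises mostly through small rises, which 5.1 read literally does not cover.

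**4. Weight of one child.** With 55 per arm (synopsis), one child handled one way or the other moves a rescue or ICU proportion by 1/55 = 1.8 percentage points.

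**The case against.** The strongest reply is that only 5.3 defines failure, in one form for both arms. Section 5.1 defines no outcome and does not say that a child suitable for flow reduction is not a failure. That stands. A reader might infer that two physicians who both follow the protocol could classify the same child oppositely. The documents do not support this: the child in step 1 scores 3 of 5 and is a failure. Arm-dependent labelling is possible because an unblinded physician ticks the failure box, and that would be so whatever 5.1 said.

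The second reply is that the rules differ in force. Reduction is only to be considered, 5.2 links it to clinical response, and 5.3 is directive. One can assess failure at 4 hours and consider weaning for the rest, and stabilized might mean settled at an acceptable level. This is a workable reading, but neither the order nor that meaning is stated, and it leaves the mismatch inside 5.3 untouched.

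The third reply is that an unchanged child need not meet all of 5.1. Take HR 150, RR 52 and SpO2 96% on a mask at 6–10 L/min. Appendix 3 gives 1 + 1 + 0 + 4 = 6 at 3 to under 12 months and 2 + 1 + 0 + 4 = 7 from 1 year, before respiratory effort, capillary refill and blood pressure are scored. Section 5.3 brings in the escalation decision at PEWS 7 or above. The oxygen item also rises once treatment starts, so PEWS measured against a pre-treatment value may not have stabilized. This stands too: it cannot be said that every unchanged child satisfies both rules.

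**Conclusion.** The point holds as a conflict over action. A child unchanged in HR, RR and CRS is a failure directed to rescue. The arm-specific lines do not describe that child, and on the natural but undefined reading of stabilize, the same three signs support considering less flow. The mismatch inside 5.3 does not depend on that reading.

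The number of children affected cannot be derived from the documents. A reader might take 18–22% as the share caught in the contradiction. It is not: it is conditional on no true change, rests on assumed SDs and CRS probabilities, and mostly counts signs that rose slightly. Under the same assumptions, exactly unchanged HR and RR with CRS not lower occurs in about 0.2–0.5%. Neither range estimates the trial's failure proportion, because the share of children with no true change is unknown.

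This should be fixed. Four-hour failure, rescue and ICU admission are compared between arms without blinding, but they are safety outcomes; the primary outcomes are the three times in 2.2.

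**What to change.** - **Protocol wording.** Reconcile 5.1 and 5.3 so that the flow-reduction condition, the failure definition and the group described as deteriorating do not point the same child to opposite actions. State the order in which the rules are applied. Which clinical rule applies is for the investigators to settle.
- **Outcome derivation.** Derive 4-hour failure in both arms from recorded HR, RR, CRS, SpO2 and pCO2, not from the yes/no tick. HR, RR, CRS and venous gases are scheduled at 4 hours, and the CRF grid has columns for these and for SpO2.
- **CRF.** Criterion 3 also needs the repeat SpO2 readings and the FiO2 or flow, which the grid does not show. Add them, or state that criterion 3 is taken from the chart.
- **Supporting table.** Show by arm the failures met only through unchanged values, separately from those with any worsening, persistent low SpO2 or carbon dioxide above 60.

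The cost is a wording amendment, one derived variable, a few CRF fields and one extra table.

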2.2 Primary Objectives

- ✓ The median time it takes for HR to reach its normal range for age (hour)
- ✓ The median time it takes for RR to reach its normal range for age (hour)
- ✓ The median time it takes for CRS to regress from severe [scores of 9-12] to moderate [scores of 5-8] bronchiolitis, or from moderate [scores of 5-8] to mild [scores of 0-4] bronchiolitis (hour)

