7.2 Data Analysis Methods

Categorical and continuous variables will be expressed as frequency (percentage) and median (IQR). Between groups, we will use the Mann-Whitney-U test for comparing the time of success for HR, RR, and CRS (SPSS Inc., version 25.0, Chicago, IL, USA). The longitudinal analysis part of the study will be performed non-parametrically with the Brunner Langer model for CRS conducted with a linear mixed model in a parametric way for HR and RR. Brunner Langer model (F1-LD-F1) is applied using web-based software (R software, version 3.5.2, package: nparLD, R Foundation for Statistical Computing, Vienna, Austria; <http://r-project.org>). The PROC MIXED procedure in the SAS software is used (Version 9.3; SAS Institute, Cary, NC, USA) to perform linear mixed models in which subjects will be included as random effects. When there is a significant interaction effect in the longitudinal analysis ($P < .1$), the time effect will be analyzed in each group, and groups will be compared at baseline and following time points (the baseline was subtracted from these time points). The proportions of the treatment failure at 4 hours, rescued patient, ICU admission, and AE are analyzed using Fisher's Exact test and given with odds ratio (OR) and 95% Confidence Interval (CI). We will perform intention-to-treat and per-protocol approaches for all outcomes. The time of success for HR, RR, and CRS outcomes will be analyzed using the PP approach. A 2-sided $P < .05$ defines statistical significance.

Statistical Analysis Plan

The biostatistician in the study, which has blinded to allocation, will perform the analysis. An interim analysis will not be performed. If substantial evidence of increased risk of harms ($p < 0.001$) observed in both groups, stopping rules will be used with the biostatistician's advice. Intention to treat and per-protocol approaches will be conducted if necessary.

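### The plan does not say how a primary recovery time reached after treatment failure or rescue is handled, and it does not rule out readings taken during ventilation

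*Combined protocol and SAP*

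**What the plan says.** Section 2.2 defines the primaries as times, in hours, to HR in the normal range for age, to RR in the normal range for age, and to a one-class fall in CRS. No condition is placed on the device in use or on unassisted breathing.

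Section 5.3 sets the rescue. In the experimental arm, "Children who deteriorate on HFNCOT are admitted to the ICU for IMV as a rescue treatment". Children who deteriorate on the mask "will receive HFNCOT (at 2 L*kg/min) as a rescue treatment in the ward or be transferred to the ICU for IMV".

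Failure does not end observation. The footnote to the schedule of observations reads: "If the patient was not discharged after 96 hours, the procedures mentioned above were continued". The one censoring rule, in 3.4, concerns withdrawal: "Data generated by the drawn infant/s will be censored at the time of withdrawal".

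On analysis, 7.2 states: "Between groups, we will use the Mann-Whitney-U test for comparing the time of success for HR, RR, and CRS". It then says: "We will perform intention-to-treat and per-protocol approaches for all outcomes". The next sentence assigns the times of success to the per-protocol (PP) approach. The Statistical Analysis Plan paragraph that follows says both approaches will be used if needed. Section 3.4 describes PP only as patients who adhered to their protocol.

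**The concern.** A child who fails high flow and is ventilated may show an in-range RR or HR at the next assessment. On a ventilator, RR largely reflects machine settings and HR can fall with sedation. That is general clinical knowledge, not something the protocol states. A child who fails the mask may recover on high flow, which is the comparator. The text does not say whether either time is the child's primary outcome.

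The two analysis sets lead to different answers. Under intention-to-treat (ITT), either time could be taken as recovery for the randomised arm. Under PP, everything turns on whether a rescued child is adherent. Rescue is itself a protocol step, so the child may stay in with that time. If the child is removed instead, the worst courses are excluded after randomisation. All three primaries are exposed to this choice, and in an open-label trial it should not be made after the data are seen.

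**Working it through.** **The plan's own figure.** 3.1 and 7.1 raise 100 to 110 for 10% attrition: 100 × 1.10 = 110 (dividing by 0.90 gives 111.1, or 112 as two equal arms). This figure does not depend on how rescue is handled. 110 children give 55 per arm.

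**What one child can do.** The Mann-Whitney win probability is U/(55 × 55). One child enters 55 of the 3,025 pairs, so moving that child from losing every pair to winning every pair changes it by 55/3,025 = 1/55 = 0.018. This is an upper bound.

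A child who fails at 4 h cannot reach it through a later reading, because the next scheduled assessment is at 12 h. Assume recovery times in the other arm are log-normal with median 12 h and log-SD 1, with no failures there:
- share later than 12 h: 0.50
- share recorded at the 12 h visit (a tie): 0.50 − Φ(ln(4/12)) = 0.50 − 0.136 = 0.364
- shift: (0.50 + 0.364/2)/55 = 0.682/55 = 0.0124, about 1.2 points

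**Benchmarks.** The pilot differences and SDs are not given, so I back-solved the t-test effect from each stated total (two-sided 0.05, 80% power) and converted it by Φ(d/√2):
- CRS, 100 children: d = 0.566, Φ(0.400) = 0.655, a shift of 15.5 points
- RR, 38 children: d = 0.934, Φ(0.660) = 0.745, about 24.5 points
- HR, 43 children: d = 0.875, Φ(0.619) = 0.732, about 23 points

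**Illustration of three handling rules.** 4,000 simulated trials, 55 per arm, scheduled visit times. Every input here is an assumption: the log-normal times above; failure at random at 4 h; mask failures then recover like high-flow children; high-flow failures are read as in range at 12 h on a ventilator. Cells show the rejection rate and, in brackets, the probability that the mask time is longer.

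| Failure, mask / high flow | Effect (SD) | Times as recorded | Failure ranked worst | Failures excluded |
|---|---|---|---|---|
| 10% / 10% | 0 | 0.089 (0.529) | 0.043 (0.500) | 0.051 (0.500) |
| 30% / 10% | 0 | 0.153 (0.549) | 0.465 (0.600) | 0.049 (0.500) |
| 10% / 20% | 0 | 0.153 (0.547) | 0.161 (0.450) | 0.058 (0.500) |
| 10% / 10% | 0.56 | 0.825 (0.649) | 0.580 (0.616) | 0.740 (0.644) |
| 30% / 10% | 0.56 | 0.844 (0.652) | 0.952 (0.689) | 0.682 (0.643) |
| 10% / 20% | 0.56 | 0.854 (0.653) | 0.161 (0.553) | 0.727 (0.644) |

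Three cautions apply. Where failure rates differ, the worst-rank rejections at zero effect reflect a real difference in failure, not a false positive. The excluded column looks unbiased only because failure was drawn at random; if the sickest children fail, it would not be. No mask failure goes to IMV in this set-up, so it shows the asymmetry at its strongest.

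The table shows that the rule matters. With 10% mask and 20% high-flow failure and no effect, the direction reverses between the first two rules (0.547 against 0.450). At an effect of 0.56 SD and the same failure rates, the rejection rate runs from 0.161 to 0.854.

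**The case against.** A reader might infer that the plan counts ventilated or rescued recoveries as successes. It does not say so; it is silent, and 7.2 assigns these times to PP. If rescued children are treated as non-adherent, their times never enter, and the problem becomes exclusion of failures. This stands, and it is why the defect is an unstated rule rather than a stated wrong one.

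A reader might also infer that ventilation flatters the high-flow arm on every primary. The documents do not support that. Mask failures can go to IMV too. In Appendix 1 a child who is drowsy or not vocalising gets the maximum dyspnoea score, so CRS is not clearly improved by IMV. That study readings are taken in the ICU is itself an inference: section 5 places the case report form in the ED and the pulmonology unit.

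Comparing the two strategies with rescue included is a legitimate treatment-policy question. Section 2.1 asks about the acute admission, and the definitions make high flow the mask arm's first-tier rescue. Ranking every escalation worst is debatable: it puts ward high flow level with ICU ventilation, escalation is an open-label clinician decision, and power in the illustration falls from 0.825 to 0.580 at 10% failure in both arms. This also stands, so I do not press worst rank as the primary analysis.

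None of this supplies the missing rule for a reading taken during IMV, or says who belongs in the PP set.

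**Conclusion.** The concern holds as a gap in the endpoint and analysis-set definitions. Applied literally, the plan allows an HR or RR read during IMV to close a primary time, and its ITT and PP sentences do not settle what happens to rescued children.

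The size is not determined, because no failure rate is given. The bound is 1.8 points of win probability per misranked child, and about 1.2 points for a 4 h failure under the assumed recovery times. A reader might multiply the bound by five children (5/55 = 9.1 points) and set it against 15.5 points. Five is an assumption, the best rank is out of reach after a 4 h failure, and 15.5 points belongs to CRS, whereas the ventilator problem mainly concerns RR and HR, where the benchmarks are about 24.5 and 23 points. Nor do the documents support saying that the study question goes unanswered. The supported conclusion is that the result can depend on a choice the plan has not made, and that the choice should be fixed before analysis.

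**What to change.** In 2.2 and 7.2:

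1. HR, RR and CRS values taken during IMV never count as recovery, in either arm.
2. A child who goes to IMV before meeting the criterion stays in the analysis of the randomised arm as not recovered at that point.
3. Name one primary analysis set, ITT, for the times of success, and state whether rescued children belong to the PP set. Reconcile the Statistical Analysis Plan paragraph with this.
4. Keep the treatment-policy time, in which recovery after ward rescue high flow counts for the randomised arm. Add an analysis that ranks any escalation before recovery worst. State in advance which of the two is primary.

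The rank test, visits and sample size are unchanged. The cost is in data: the case report form has one study-device box and only yes/no entries for ICU transfer and 4-hour failure. The date and time of escalation, and the support in use at each assessment, must therefore be taken from the clinical notes. The worst-rank analysis may also lose power, as the illustration shows.
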